#### 8.2.1. Registration criteria

Patients must meet all of the following inclusion criteria to be eligible for inclusion in the study:

- The purpose of treatment with this drug is ATTR-CM.

\*Patients who have participated in clinical studies of ATTR-CM and continue to receive treatment of ATTR-CM are eligible for inclusion.

Refer to the latest package insert of this drug for “indications” and “dosage and administration” when this drug is administered. The descriptions on ATTR-CM are excerpted and shown below:

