**8.2.2. Exclusion criteria**

No exclusion criteria are set for this study.

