**Figure 1. Observation period for each booklet**

**Figure 2. Setting of observation period for transferred patients**

### 8.3. Variables

This study will be conducted according to the following schedule of observation.

For patients transferred from the clinical trial, the first administration day of a marketed product of this drug will be the first day of administration of this drug.

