### 8.3.1. Patient characteristics

1. Enter the information at the start of administration of this drug into the registration form.

- a. Site information (if the study is conducted using paper CRFs)
- b. ID number
- c. Gender
- d. First day of treatment with this drug for ATTR-CM (first administration day of a marketed product of this drug for patients transferred from clinical trials, hereinafter the same)
- e. Identification of transferred patients (in the case of transferred patients, enter the patient registration number of the original site)
- f. Usage experience of this drug [administered this drug for the first time, transferred from clinical trials, or in treatment for transthyretin-type familial amyloid polyneuropathy (TTR-FAP) but also started to receive the treatment of ATTR-CM] (no entry is necessary for transferred patients)

If the patient is a transferred patient and the patient registration number of the original site has been entered, the entries for the following items g. to i. are not necessary (the entries are necessary even for the transferred patient if the patient registration number of the original site is not clear)

- g. Birth year (known at the start of administration of this drug) (if the birth year cannot be disclosed, enter the age at the start of administration of this drug)
  - h. Disease type of ATTR-CM (wild-type, variant, or unknown)
  - i. Severity of heart failure (NYHA Functional Classification)
2. The following will be recorded in CRF at the start of administration of this drug. If the contents of the registration form have been reflected, the investigator will check the contents again and make corrections as necessary.
- a. ID number
  - b. Gender

- c. Identification of transferred patients (in the case of transferred patients, enter the patient registration number of the original site)
- d. Usage experience of this drug (administered this drug for the first time, transferred from clinical trials, or in treatment for TTR-FAP but also started to receive the treatment of ATTR-CM) (no entry is necessary for transferred patients)

If the patient is a transferred patient and the patient registration number of the original site has been identified, the entries for the following items e. to o. are not necessary (the entries are necessary even for the transferred patient if the patient registration number is not clear)

- e. Birth year/age
- f. Inpatient/outpatient status
- g. Height (cm)
- h. Body weight (kg)

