5.2. Efficacy Analysis Set

The efficacy analysis set is defined as the population of patients in the safety analysis set, excluding those who meet any of the following conditions:

8. Efficacy cannot be evaluated appropriately because of insufficient conditions for efficacy evaluation (Description in the report: “Efficacy evaluation not possible”).

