5.4. Subgroups

Subgroup analyses of safety will be performed for the following patient characteristics and other factors. For the patient characteristics and other factors with those of specific categories underlined, a risk ratio will be calculated using each underlined category as the reference.

- Inpatient/outpatient status at the first prescription [inpatient, outpatient]
- *Severity of liver impairment [absent, mild, moderate, severe]
- Liver impairment [absent, present]
- Renal impairment [absent, present]
- Age [<15 years, ≥15 to <65 years, ≥65 years]
- *TTR genetic variant [wild-type, variant]
- NYHA functional classification [Class I/II, III/IV]
- NYHA functional classification [Class I, II, III, IV]
- Concomitant medication [absent, present]
- Non-drug therapy (device therapy) [absent, present]

- Complication [absent, present]
- Gender [male, female]
- Usage experience of this drug (administered this drug for the first time, transferred from clinical trials, transition from the treatment of ATTR-PN)

*Evaluation of the important missing information (safety in patients with severe liver impairment and patients with variants)

Subgroup analyses of efficacy will be performed for the following patient characteristics:

- TTR genetic variant [wild-type, variant]
- NYHA functional classification [Class I/II, III/IV]
- NYHA functional classification [Class I, II, III, IV]

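### The effectiveness analyses pool patients with earlier use of the drug and first-time users, and none is planned by usage experience

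*SAP*

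**What the plan says.** **Who enters.** Protocol 8.2.1 states: "Patients who have participated in clinical studies of ATTR-CM and continue to receive treatment of ATTR-CM are eligible for inclusion". Protocol 8.2.2 adds: "No exclusion criteria are set for this study". Protocol 8.3.1 records usage experience in three categories: first-time use, transfer from a clinical trial, and patients under treatment for TTR-FAP "but also started to receive the treatment of ATTR-CM".

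**Day 1.** For trial transfers, Protocol 8.3 says that "the first administration day of a marketed product of this drug will be the first day of administration of this drug". For other patients, including those with TTR-FAP, the registration form takes the "First day of treatment with this drug for ATTR-CM" (Protocol 8.3.1).

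**Baseline.** SAP Appendix 1 (A1.1) takes laboratory and effectiveness baselines from the 30 days up to and including Day 1. Baseline NYHA class comes from the case report form entry for the start of treatment.

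**Effectiveness population.** SAP 5.2 removes patients from the safety set on one ground only: "Efficacy cannot be evaluated appropriately because of insufficient conditions for efficacy evaluation". It states no rule on prior use.

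**Subgroups.** The safety list in SAP 5.4 includes "Usage experience of this drug (administered this drug for the first time, transferred from clinical trials, transition from the treatment of ATTR-PN". The effectiveness list, opened by "Subgroup analyses of efficacy will be performed for the following patient characteristics", has TTR variant status and two NYHA groupings.

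**Models.** The MMRM in SAP 8.2.4.2 has terms for variant status, NYHA group, time point and baseline value. The same section takes the MMRM out of the subgroup analyses. Survival in SAP 8.2.4.3 runs from the start of administration. SAP 8.2.4.4 stratifies Kaplan-Meier estimates by the factors of Section 5.4 without saying which of its two lists is meant.

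**The concern.** All three effectiveness endpoints in SAP 6.2 are measured from Day 1: NYHA change, biomarker change and survival time. For a first-time user, Day 1 is the start of treatment. For a trial transfer, it is the first marketed dose after time in a trial. For a TTR-FAP patient already taking the drug, it is the date on which ATTR-CM treatment began. In both latter cases the baseline can be an on-treatment value, so a later change no longer means change since starting the drug. Trial transfers also had to be alive at roll-over, which a first-time user did not.

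A pooled mean change or survival curve then describes a mixture whose composition affects the answer. Effectiveness data are part of the approval conditions, and Protocol 8.5.2 expects 300 patients to allow effectiveness to be confirmed to some extent. A reader will naturally take the pooled result as what happens after treatment starts.

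**Working it through.** **1. The plan's own figures.** Protocol 8.5.2 takes 750 × 0.40 = 300 patients. It puts the chance of at least 10 hepatotoxicity cases at about 98% for a true incidence of 5.88%. The exact binomial gives P(X ≥ 10 | n = 300, p = 0.0588) = 0.984, so the statement reproduces. It concerns safety and is untouched by this point. The documents give no effect size, standard deviation or precision target for effectiveness.

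**2. Where usage experience appears.**

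| Place | Usage experience used? |
|---|---|
| Protocol 8.3.1, collection | Yes |
| SAP 8.2.2.1, characteristics tables (safety and efficacy sets) | Yes |
| SAP 5.4, safety subgroups | Yes |
| SAP 5.4, effectiveness subgroups | No |
| SAP 8.2.4.1, NYHA tables | No |
| SAP 8.2.4.2, biomarker summaries and MMRM | No |
| SAP 8.2.4.3, survival | No |
| SAP 8.2.4.4, Kaplan-Meier strata | Not by name |

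**3. Illustration of size.** The documents do not give the prior-user share f. I assume f = 5% to 40% of 300.

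- *Biomarker change.* Let prior users show k times the first-time-user change. Pooled change ÷ first-time-user change = (1 − f) + f·k.
- *Survival at 30 months.* Assume 70% in first-time users and either 60% or 80% in prior users. Pooled survival = 0.70(1 − f) + 0.60f or 0.70(1 − f) + 0.80f.
- *Cost in precision.* Restricting to first-time users leaves 300(1 − f) patients and widens intervals by a factor of 1/√(1 − f).

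| f | First-time users | Change ratio, k = 0 | Change ratio, k = 0.5 | Pooled survival, prior users 60% / 80% | Interval widening |
|---|---|---|---|---|---|
| 5% | 285 | 0.95 | 0.975 | 69.5% / 70.5% | 1.03 |
| 10% | 270 | 0.90 | 0.95 | 69% / 71% | 1.05 |
| 20% | 240 | 0.80 | 0.90 | 68% / 72% | 1.12 |
| 40% | 180 | 0.60 | 0.80 | 66% / 74% | 1.29 |

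For scale, ignoring censoring, the 95% half-width around 70% survival with 300 patients is 1.96 × √(0.7 × 0.3 / 300) = 5.2 points. The survival shifts above (0.5 to 4 points) are smaller than that. The biomarker ratio is affected more, in proportion to f.

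**The case against.** The other side has several sound points.

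- *The study is descriptive.* The stated objective is long-term safety, SAP 4 calls the study non-confirmatory, and Protocol 8.9 declares the lack of a control group and limited handling of confounding. This stands: interpretation is affected, error rates are not.
- *The SAP follows the protocol.* Protocol 8.7 names only genotype and NYHA class for subset analyses. True, but the SAP already adds other factors for safety, usage experience among them.
- *The share will be visible.* SAP 8.2.2.1 tabulates usage experience for the efficacy set. That shows how many prior users there are, not how their results differ.
- *Genotype already separates some of them.* TTR-FAP is familial, so the variant stratum probably holds most of those patients. It does not separate trial transfers.
- *Further analyses are allowed.* SAP 8.2.4.4 permits them but commits to none, and its exploratory results are reported only if judged important.
- *Section 8.2.4.4 could mean both lists.* The separate effectiveness list makes this the less natural reading. If it is intended, the text should say so.

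Stronger readings that a reader might infer are not supported:

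- *That Day 1 is reset to the marketed product for all prior users.* This is stated only for trial transfers.
- *That the survival estimate is invalid through left truncation.* Time zero is defined as the start of administration in this study and everyone is followed from it. The population is heterogeneous; the estimate can still be computed and described.
- *That prior users have longer disease, or that the bias has a known direction.* The documents give neither disease duration nor prior exposure, and do not say that every transfer was on active drug at entry.
- *That first-time users should replace the pooled set as the main result.* Protocol 8.7 builds the effectiveness set from the safety set, and the approval conditions call for an all-patient survey. SAP version 6.0 (23 January 2025) already postdates the planned database release (November 2024), so a new headline population would look post hoc.

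**Conclusion.** The point holds as a low-cost improvement in interpretability. Prior users are eligible, their baseline can be on-treatment, and no planned effectiveness analysis separates them by usage experience, although the variable is collected and used for safety. Trial transfers are the group left wholly unseparated; TTR-FAP patients are probably separated in part by genotype.

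The size cannot be derived from the documents. The ranges in the table rest entirely on the assumed share (5% to 40%), the assumed relative change (k = 0 or 0.5) and the assumed survival rates. The direction for survival is open. If prior users are few, the effect is small, but the pooled tables alone cannot show how their results differ.

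**What to change.** 1. In SAP 5.4, add *Usage experience of this drug* (first time, transferred from trials, transition from ATTR-PN) to the effectiveness subgroup list.
2. In SAP 8.2.4.4, name it as a Kaplan-Meier stratification factor and state which list in 5.4 applies.
3. In SAP 8.2.4.2, add a supplementary MMRM in first-time users. The change to 5.4 alone would not reach the MMRM, because that section excludes it from subgroup analysis.
4. Keep the protocol-defined pooled set as the main result, show first-time users beside it, and label the added analyses with the date they were specified.

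The cost is SAP wording and reruns of existing tables; no new data are needed. The downsides are a few more tables, prior-user strata that may be small, and wider intervals in the first-time-user analysis (by a factor of 1.03 to 1.29 over the assumed range).

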6. ENDPOINTS AND COVARIATES

6.1. Safety Endpoints

- Adverse reactions: Adverse events assessed as related to this drug by the physician
- Adverse events: Adverse events of any causality
- Serious adverse events or adverse reactions: Adverse events or adverse reactions assessed as serious by the physician
- Safety specifications: Events to be handled as safety specifications will be specified according to the latest version of the “Rationale for Safety Specifications and Events to be Defined based on the Risk Management Plan.”
- Important potential risks:
 - Hepatotoxicity
 - Hypersensitivity reactions
 - Reproductive and developmental toxicity
 - Infection
 - Incorrect product selection between Vyndaqel and Vynmac
- Laboratory tests

6.2. Efficacy Endpoints

- Change in NYHA functional classification
- Change in cardiac biomarker values (NT-pro BNP, BNP, troponin I, troponin T)
- Survival time

6.3. Other Endpoints

Not applicable.

7. HANDLING OF MISSING DATA

If treatment with this drug is continued even after the end of the observation period and the end date of treatment is missing, the end date of observation will be handled as the end date of treatment in this study.

If the seriousness, causal relationship, and action taken and outcome regarding adverse events are missing, these data will be handled as “unknown” for tabulation.

For the efficacy endpoints and laboratory test values, if there is no measurement within the time window for each evaluation time point (Appendix 1), data will be handled as missing, and the missing data will not be complemented.

The strategy for handling data with uncompleted cleaning is described below:

- Items of missing data: The items will be handled as missing (category of categorical variables is “unknown”) for both tabulation and listing.
- Items of inconsistent data: The items will be handled as missing for both tabulation and listing. However, a list of data handling should be prepared separately.
- No signature: Any entry in a case report form without the signature of the contracted physician (including a case report form with the signature of an uncontracted physician only) will be handled as missing for both tabulation and listing. If there is no date of signature in the field for the date of signature or if there is inconsistency in the date entered (e.g., date before the start date of treatment, future date), the entry in the case report form will be regarded as having no signature.

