#### 8.6. Data management

##### 8.6.1. Case report forms (CRFs)/Electronic data record

As used in this protocol, the term CRF should be understood to refer to either a paper form or an electronic data record, or both, depending on the data collection method used in this study.

A CRF is required and should be completed for each included patient. The completed original CRFs are the sole property of Pfizer and should not be made available in any form to third parties, except for authorized representatives of Pfizer or appropriate regulatory authorities, without written permission from Pfizer. The investigator shall ensure that the CRFs are securely stored at the study site in an encrypted electronic and/or paper form and will be password protected or secured in a locked room to prevent access by unauthorized third parties.

The investigator has ultimate responsibility for the collection and reporting of all clinical, safety, and laboratory data entered on the CRFs and any other data collection forms (source documents) and ensuring that they are accurate, authentic/original, attributable, complete, consistent, legible, timely (contemporaneous), enduring, and available when required. The CRFs must be signed by the investigator or by an authorized staff member to attest that the data contained on the CRFs are true. Any corrections to entries made in the CRFs or source documents must be dated, initialed or stamped "correction seal", and explained (if necessary) and should not obscure the original entry.

The source documents are the hospital or the physician's chart. In these cases, data collected on the CRFs must match those charts.

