#### **8.6.5.3. Submission**

After data entry and revision are completed, CRFs should be signed electrically by the investigator following confirmation of entry and follow-up survey.

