8.2.3. Safety analysis

All adverse reactions and adverse events occurring after the start of administration of this drug will be summarized in listings. The listings will include all events reported in this study. Safety will be evaluated using all data collected after the start of administration of this drug without classifying the data into Vyndaqel and Vynmac unless otherwise specified was added.

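### SAP 7 drops entries in CRFs left unsigned or misdated at the data cut from both tables and listings, adverse events and deaths included and with no record of what was removed, contrary to SAP 8.2.3 and more strictly than Protocol 8.6.1

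*SAP*

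**What the plan says.** SAP 7 introduces a set of rules with "The strategy for handling data with uncompleted cleaning is described below". The last of them covers "Any entry in a case report form without the signature of the contracted physician". A bracket there extends the rule to forms that someone else has signed: "including a case report form with the signature of an uncontracted physician only". Such an entry "will be handled as missing for both tabulation and listing. If there is no date of signature in the field for the date of signature", and likewise where the date is inconsistent (the SAP's examples are a date before treatment start and a future date), "the entry in the case report form will be regarded as having no signature". The neighbouring rule for inconsistent items asks for a separate list of how the data were handled. The signature rule asks for none.

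SAP 8.2.3 says of adverse reactions and events: "The listings will include all events reported in this study".

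The protocol gives more than one signature standard. Section 8.6.1, for all CRFs: "The CRFs must be signed by the investigator or by an authorized staff member to attest" that the data are true. Section 8.6.5.3, for electronic capture: "After data entry and revision are completed, CRFs should be signed electrically by the investigator". Section 8.6.8.3, for paper forms, has the investigator submit the form and does not mention a signature.

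**The concern.** The study's objective is long-term safety. Under the rule as written, a reaction or death that a site has recorded can be left out of every table and listing of the study because of an administrative defect in the form, and the report need not say so. The signatory may even be one that Protocol 8.6.1 accepts.

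The loss is not neutral for the main safety measure. Protocol 8.7 divides the number of patients with adverse reactions by the number in the safety analysis set, and an unsigned form is not among the exclusion reasons in SAP 5.1. A patient can therefore remain in the denominator after part of the numerator information has been removed.

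**Working it through.** **1. The texts side by side**

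- *Listing.* SAP 8.2.3 lists every reported event. SAP 7 makes an event on an unsigned or misdated form missing for listing. Both cannot hold for the same event, and neither section refers to the other.
- *Signatory.* Protocol 8.6.1 accepts the investigator or authorised staff. SAP 7 accepts only the contracted physician. A form signed only by authorised staff meets the first and is voided by the second. Protocol 8.6.5.3 is closer to the SAP for electronic forms. A form with no signature at all fails Protocol 8.6.1 as well.
- *Signature date.* Protocol 8.6.1 sets no condition on it. SAP 7 voids the entry if it is absent or inconsistent.
- *Backstop.* SAP 8.2.3.1.5 lists adverse reactions in patients excluded from the safety analysis set. It does not recover these events, because SAP 7 blanks them for listings too.

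**2. A patient with a valid Booklet 01 and an invalid Booklet 02**

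Booklet 02 covers Weeks 53 to 130 (Protocol Table 1). That each booklet is signed separately is inferred, not stated.

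- *Overall adverse reaction proportion:* Booklet 01 supplies drug and event information, so the patient stays in the set. Events recorded only in Booklet 02 vanish. The numerator can only fall and the denominator is unchanged.
- *Crude number and proportion of deaths (SAP 8.2.4.3):* a death recorded only in Booklet 02 vanishes in the same way. In the survival analysis the patient would be censored at the last valid confirmation of survival.
- *Onset-period table (SAP 8.2.3.1.3):* each period's denominator is the patients dosed in it. The Booklet 02 dosing record is blanked too, so the patient may leave both numerator and denominator, and the direction of error is not determined.
- *A patient with no valid booklet:* may leave the safety analysis set under criteria 4 to 7 of SAP 5.1. The documents do not settle this.

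**3. Scale**

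Inputs from Protocol 8.5: n = 300, true hepatotoxicity incidence p = 5.88%, stated probability of at least 10 cases about 98%.

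Reproducing the plan's figure: expected cases 300 × 0.0588 = 17.64; exact binomial P(X ≥ 10 | 300, 0.0588) = 0.984. This agrees with the protocol.

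Let f be the share of cases lost. The documents give no value, so f is an assumption. If the patients stay in the denominator, the expected observed proportion is 0.0588 × (1 − f). If they leave the set, n = 300 × (1 − f).

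| f | Expected proportion, patients kept | P(≥ 10), patients kept | P(≥ 10), patients leave |
|---|---|---|---|
| 0% | 5.88% | 0.984 | 0.984 |
| 1% | 5.82% | 0.982 | 0.982 |
| 5% | 5.59% | 0.974 | 0.974 |
| 10% | 5.29% | 0.958 | 0.959 |
| 20% | 4.70% | 0.901 | 0.903 |

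Linking f to Booklet 02: it spans 130 − 52 = 78 weeks, and 78/130 = 60% of full observation. If 5% to 10% of Booklet 02 forms were invalid (assumed), events were spread evenly and every patient reached Week 130, the share of events lost would be 0.60 × 5% = 3% to 0.60 × 10% = 6%. Applied to 5.88% this gives 5.88 × 0.97 = 5.70% and 5.88 × 0.94 = 5.53%. The loss counted in patients would be smaller, because a patient with another such event in Booklet 01 is still counted. Early discontinuation would also reduce Booklet 02's share of exposure.

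**The case against.** The strongest defence is that this is a residual rule, and that leaving out unattested data is a legitimate data-integrity choice. It applies only where cleaning is incomplete, and queries (Protocol 8.6.5.2 and 8.6.8.2) may clear most defects first. Electronic capture is the standard route and paper the exception (Protocol 8.6.6), and for electronic forms the protocol itself asks for the investigator's signature. The SAP's change log for version 5.0 suggests that the wording of 8.2.3 was aimed at the time window of events, so SAP 7 could be meant as the specific exception.

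Much of this stands. It limits how many forms are affected and narrows the signatory conflict to forms signed only by authorised staff and to signature-date defects. It also argues against moving unattested entries into the main tables. It does not explain why such events should be absent from listings as well, or why no count or list of them is kept. If SAP 7 is meant as an exception to 8.2.3, neither section says so.

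A reader might go further in four ways that the documents do not support:

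- *That serious events are lost altogether.* Protocol 10.1 sends serious events and exposure scenarios to the sponsor's safety unit within 24 hours. They would be missing from this study's output, not from safety surveillance. By the table in that section, non-serious events outside those scenarios have only the CRF route and are the most exposed.
- *That the patient is counted as event-free in Weeks 53 to 130.* The onset-period denominators may lose the patient too.
- *That forms with adverse events are signed later and so are preferentially lost at interim cuts.* No passage says this. Most such cuts also lie in the past: observation was to end in September 2023 and the database to be released in November 2024, before the SAP version of January 2025.
- *That 3% to 6% of reactions are lost.* That figure rests wholly on an assumed rate.

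**Conclusion.** The point holds as a conflict between texts and a gap in traceability. SAP 7 can remove reported adverse events and deaths from the study's tables and listings without a record. It contradicts SAP 8.2.3 and is stricter than Protocol 8.6.1 on signatory and signature date.

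For the overall adverse reaction proportion, the two-booklet case can produce only understatement. This assumes that booklets are signed separately and that the defect is still open at the cut. The size cannot be determined from the documents. On the assumed range, a loss of up to about 5% of cases barely changes the design's detection probability (0.984 to 0.974), and at 20% it falls to about 0.90. Few forms may be affected, but the plan gives the reader of the report no way to tell. The plan should be changed for that reason, not because a material bias has been shown.

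**What to change.** In SAP 7:

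- Exempt adverse event and death entries from being treated as missing in listings, and list them with an unsigned/misdated flag.
- Report the number of CRFs and patients affected at every data cut still to be made, including the final analysis.
- Place one supportive safety table (adverse reactions, serious adverse events, deaths) that includes the flagged entries beside the main table.
- State whether a patient with no validly signed booklet stays in the safety analysis set.

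Across documents: reconcile the accepted signatory and the signature-date condition in SAP 7, Protocol 8.6.1 and Protocol 8.6.5.3, so that a CRF validly signed under the protocol is not voided in the analysis.

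The cost is some wording, one flag variable, one count and one table. The downside is that some unattested entries appear in the listings and in one supportive table, where the flag identifies them. The main tables can keep the present rule.
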